#### 5.3 Recruitment

Participants will be randomised to one of two treatment arms. Patients in both groups will be given standard advice on leg ulcers and their management. Stratification by wound size (PUSH score up to and including 10 or PUSH score of 11 or higher) will take place.

All participants will have demographic data obtained and the following measures (table 3):

Weeks	0	2	4	6#	8	10	12#
Baseline measures (demographics,	Х						
medical history, vascular history)							
Ulcer wound status + bandage	Х			Х			Х
use status							
Ulcer size measured with wound	Х			Х			Х
grid							
PUSH score	Х			Х			Х
Visual analogue pain score	Х			Х			Х
Visual analogue pruritus score	Х			Х			Х
EQ-5D-5L	Х			Х			Х
VEINES-QoL	Х			Х			Х
Photo of ulcer (or original index	Х			Х			Х
site); subject to consent by patient							

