#### Table 3. Baseline measures

# Allowed to be up to 2 weeks early or late. For all follow-up dates, calculation is based on original enrolment date for patient, even if deviation for one or more follow-up timepoints.

The Pressure Ulcer Scale for Healing (PUSH) tool, see Appendix 1 is a standardised method of assessing and monitoring the severity and healing of both pressure ulcers and venous leg ulcers (Stotts et al, 2001; Ratliff & Rodeheaver 2005). Concerns have been raised regarding the criterion validity and intra-rater reliability of the tool (Pillen et al 2009) however in the absence of other valid tools it provides a comprehensive parallel assessment of the ulcer along with measuring size alone.

VEINES-QoL is a patient reported outcome measure score that focuses on lower limb health, and can be used in patients both with, or without a leg ulcer (Launois 2015)

During the recruitment process the research team acts as a contact point and coordinator for patients requiring information and support. If concerns are raised on participants (mental) wellbeing

based on the home visits or outcome of the assessments, referral of patients/families on to other professional agencies will be done as appropriate and according to the Trust guideline.

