#### 5.4 Follow-up and Standard care

Patients are in the study for the planned 12 weeks, even if the index leg ulcer has healed prior to that time point. Apart from the specific research measurements and assessments, the patient will be followed up as they would in normal clinical practice. The vascular or community nurse will redress the leg ulcer as per routine care, and will conduct the measurement of the leg ulcer (grid measurement and PUSH score). The researcher will visit the patient at baseline, week 6 and 12 of study participation to randomise the patient and conduct the questionnaires.

Patients identified in the community (primary care or non-vascular surgery dept) can be invited to participate in the study via the vascular surgery department.

Standard wound care will be provided throughout the trial period, as well as meeting any other medical needs that arise. The SIGN guidelines for leg ulcer care form the framework for management of the leg ulcers (https://www.sign.ac.uk/media/1058/sign120.pdf).

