#### 5.5 Outcome measures

#### 5.5.1 Primary outcome measures

Wound status (healed vs non-healed)

In line with the definition used by the VENUS6 trial team, the primary outcome of this trial is time to healing of the reference ulcer, and the definition is: complete epithelial cover in the absence of a scab (eschar) with no dressing required. There is no minimum length of time that the index site has to have been in said condition for when participant present for follow-up study visit.

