## 8.3 Secondary outcome statistics

To evaluate the effect of the different reduced compression bandages on leg ulcer healing, data from the two treatment arms will be compared.

Ulcer healing and more general health measures is assessed by the following parameters:

- Ulcer status (healed vs non-healed)
- Ulcer size (cm^2, measured with wound grid)
- PUSH score
- Visual analogue pain score
- Visual analogue pruritus score
- VEINES-QoL
- EQ-5D-5L

To assess the Ulcer size, PUSH score, visual analogue pain score, and visual analogue pruritus score, which are measured every 6 weeks, per treatment arm the average difference between time points will be calculated per treatment group (Wilcoxon test). To compare between the groups, Mann-Whitney U-test will be applied.

To measure patient-reported outcome measures on quality of life (VEINES-QoL and EQ-5D-5L) at baseline, week6 and week 12; the Wilcoxon test will be applied within treatment arms (over time) whereas the Mann-Whitney U-test will be performed between treatment arms. Data of the two treatment arms will be compared by applying the Mann-Whitney U-test.

Subject to sufficient data being available, Cox proportional hazards regression analysis will be conducted to investigate the role of the compression bandage itself and other covariates in leg ulcer healing rates. Other covariates include: leg ulcer size and chronicity at baseline, patient age, ulcer aetiology (pure venous vs other), absence/presence of co-morbidities, ulcer location, history of recurrent ulcers.

The following descriptive statistics will be reported on where possible:

- Number of patients screened
- Number of patients eligible/ineligible, and percentage of patients consented into the trial
- Number of patients completed the trial/discontinued (plus reasons if discontinued)

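### Section 8.3 plans standard Cox regression for healing that is observed only at two windowed visits; if visit dates serve as event times and visit timing differs by arm, the hazard ratio could show a false bandage effect

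*Protocol*

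**What the plan says.** - **The model.** Protocol section 8.3 (Secondary outcome statistics), on condition that there are enough data: "Cox proportional hazards regression analysis will be conducted to investigate the role of the compression bandage itself and other covariates". The covariates follow: "Other covariates include: leg ulcer size and chronicity at baseline, patient age, ulcer aetiology (pure venous vs other"), then comorbidity, ulcer location and history of recurrent ulcers. The section names neither the event time nor interval censoring.
- **When healing is observed.** In Table 3 (section 5.3) the row beginning "Ulcer wound status + bandage" is marked at weeks 0, 6 and 12 only; weeks 2, 4, 8 and 10 are empty. Section 5.4 agrees: "The researcher will visit the patient at baseline, week 6 and 12 of study participation".
- **Visit windows.** The footnote to Table 3 says of the week 6 and week 12 visits: "Allowed to be up to 2 weeks early or late". All follow-up dates count from enrolment.
- **What counts as healed.** Section 5.5.1 judges the condition found at the visit: "There is no minimum length of time that the index site has to have been in said condition". No healing date is among the listed measures.
- **Blinding.** Section 6.1.1 says that participants cannot be blinded and that the statistical analysis is blinded to allocation.

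**The concern.** Standard Cox regression needs a time for each event and uses the order of those times. Here the data say only that an ulcer closed before the first follow-up visit, between the two visits, or not by the last one. Some date must stand in for the healing date, and the obvious candidate is the visit date. Patients are then ranked by when they were seen as well as by when they healed. If one arm tends to be seen earlier, its healings are dated earlier, and its patients leave the risk set earlier, even when healing is identical.

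At stake is the interpretation of the bandage hazard ratio, the only planned regression estimate of the bandage effect on healing adjusted for other covariates. The same mechanism applies to any covariate that is related to visit timing.

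**Working it through.** The protocol gives no event time, hazard ratio or power for this model, so there is no figure of its own to reproduce.

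**Step 1. What is observed.** The windows are 6 ± 2 = weeks 4 to 8 and 12 ± 2 = weeks 10 to 14. The interval between visits can be as short as 10 − 8 = 2 weeks or as long as 14 − 4 = 10 weeks. An ulcer healed at the first visit closed at some time in the preceding 4 to 8 weeks.

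**Step 2. Assumptions.** From the protocol: 46 per arm, and 50% healed by week 12 (the Coban2 rate in Table 4), applied here to both arms so that the true HR is 1. Assumed, because the protocol gives no value: exponential healing, so the unhealed share is S(t) = 0.5^(t/12), and the gaps in mean visit timing, shown as a range.

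**Step 3. One case by hand.** Let Andoflex visits average weeks 5.5 and 11.5, Coban2 visits weeks 6.5 and 12.5, each spread ± 0.5 week. All visits stay inside the windows.

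- Healed at first visit: Andoflex 46 × (1 − 0.5^(5.5/12)) = 46 × 0.272 = 12.5; Coban2 46 × 0.313 = 14.4.
- Healed at second visit: Andoflex 46 × (0.728 − 0.515) = 9.8; Coban2 46 × (0.687 − 0.486) = 9.3.

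The Cox score at HR = 1 adds (1 − s) for each Andoflex event and −s for each Coban2 event, where s is the Andoflex share of those still at risk. Each event adds s(1 − s) to the information. In visit-date order:

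| Events | Course of s | Mean s | Score | Information |
|---|---|---|---|---|
| Andoflex, first visit | 0.50 to 0.42 | 0.463 | 12.5 × 0.537 = +6.7 | 12.5 × 0.248 = 3.1 |
| Coban2, first visit | 0.42 to 0.51 | 0.465 | −14.4 × 0.465 = −6.7 | 14.4 × 0.248 = 3.6 |
| Andoflex, second visit | 0.51 to 0 | 0.318 | 9.8 × 0.682 = +6.7 | 9.8 × 0.196 = 1.9 |
| Coban2, second visit | 0 | 0 | 0 | 0 |

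The score is 6.7 and the information 8.6. The one-step log HR is 6.7/8.6 = 0.78, so HR = exp(0.78) = 2.18, with z = 6.7/√8.6 = 2.3. The imbalance arises at the second visit: every Andoflex patient has healed or been censored before the first Coban2 second-visit healing, so those 9.3 events count for nothing.

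**Step 4. Simulation.** True HR 1, 46 per arm, Cox with Efron ties, two-sided 5%, 1,000 trials per fully tabulated row. Cells show median HR and false-positive rate. The interval-censored model is a Weibull proportional hazards model on (last unhealed visit, first healed visit].

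| Mean gap (Andoflex earlier), spread | Cox, visit date | Cox, nominal week 6 or 12 | Interval-censored PH |
|---|---|---|---|
| None, ± 2 weeks | 1.02, 5.4% | 1.00, 5.2% | 1.02, 4.8% |
| 0.5 week, wide | about 1.27, 10% | – | – |
| 1 week, ± 1.5 | 1.46, 24% | 0.91, 6% | 1.01, 4.2% |
| 1 week, ± 0.5 | 2.12, 59% | 0.89, 6% | 1.00, 5.6% |
| 2 weeks, ± 0.5 | 1.80, 42% | 0.83, 7% | 0.99, 4.1% |
| 4 weeks (maximum) | 1.40, 17% | 0.69, 22% | 0.99, 5.0% |

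The fourth row agrees with the hand calculation. Cox on the true healing times gives HR 1.00 to 1.02 and 4% to 6% error throughout, so the fault lies in the substituted event time. A complementary log-log model with period and log interval length as offset gives HR about 1.0 and about 4% to 7% error.

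The visit-date bias does not grow steadily with the gap. Once the arms no longer overlap, a wider gap reorders nothing further but gives the early arm less time to heal. At the maximum gap the last visits are at weeks 10 and 14, with 1 − 0.5^(10/12) = 44% and 1 − 0.5^(14/12) = 55% healed. That difference also explains why nominal-week coding errs in the opposite direction.

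**The case against.** The strongest reply is that the false effect needs two things the protocol does not state: that visit dates are the event times, and that visit timing differs by arm. Section 8.3 names no time scale. Follow-up is counted from enrolment in the same way for both arms, and with equal timing the visit-date model is sound under the null (HR 1.02, 5.4%). Nominal weeks leave the error near 6% at a 1-week gap. All of this stands. A reader might infer that the hazard ratio will be distorted; the documents support only that it could be.

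Appendix 2 requires a date and reason when bandaging is stopped, including for a healed wound, and nurses redress the ulcer routinely. These sources could date some healings approximately. The protocol does not define either as an assessed healing date, and the Appendix 2 date also covers stops and pauses for other reasons.

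An analysis plan that is not shown could settle time scale and ties. But 8.3 already names the model, and no later plan can recover dates that were never collected. The condition of sufficient data concerns quantity and does not address interval censoring.

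Two further inferences are tempting. Section 5.5.1 says that "the primary outcome of this trial is time to healing of the reference ulcer", which might suggest that the primary result is at risk. The sub-heading there, the primary objective, the sample size and section 8.2 all use healed or not healed at week 12, so that sentence is a separate wording matter. The covariate list might also suggest an overfitted model. Section 8.3 does not fix how covariates such as location are coded and makes the model conditional on sufficient data, so a count of events per parameter cannot be derived from it.

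**Conclusion.** The point holds in a conditional form. Healing time is interval-censored by design, and 8.3 names a model that does not handle this and does not say which time it uses. If visit dates are used and timing differs by arm, the bandage hazard ratio could be seriously wrong: about 1.27 with 10% error at a half-week mean gap with wide spread, and about 1.5 to 2.1 with roughly 25% to 60% error at one week, depending on spread. With nominal weeks the bias at a 1-week gap is smaller and reversed (HR about 0.9), so the unstated choice of date can change the direction of the error.

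These sizes rest on exponential healing at 50% by week 12 in both arms and on assumed timing gaps; they illustrate what the permitted windows allow and do not forecast this trial. The analysis is secondary and conditional, and this model does not enter the week-12 non-inferiority test. The change is worth making because a method that avoids the problem costs little.

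**What to change.** In section 8.3, replace standard Cox regression with one of these, using actual visit dates:

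- an interval-censored proportional hazards model, in which each ulcer contributes the interval from the last visit unhealed to the first visit healed, or is right-censored at the last visit; or
- a discrete-time binary model with complementary log-log link, a term for period (baseline to first visit, first to second visit) and log interval length as offset.

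Both still yield a hazard ratio for bandage. Also report the distribution of actual visit times by arm at weeks 6 and 12.

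Alternatively, keep Cox regression, add one data field for the date on which closure is first seen at a routine dressing change, and state that this date is the event time.

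The cost is a small change of analysis wording and possibly a different procedure or package from the one named in section 8.2; the alternative adds one date per healed ulcer. The choice of covariates is left to the sponsor.

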## 9. DATA HANDLING AND MONITORING

Data arising from this study is confidential. Identifiable information can only be accessed by delegated members of the study team. Anyone in the research team who does not have a substantive contract with North Cumbria Integrated Care NHS Foundation Trust will need to apply for a letter of access via the NIHR research passport scheme, should they require access to identifiable study data.

Patient identifiable data will only be used within each respective Trust and by the core research team. All identifiable data is stored on password protected NHS computer systems. Anonymised data will be shared and stored using security-enabled systems such as password-protection and encryption of e-mails and files. The requirements of the Data Protection Act, GDPR, and NHS Code of Confidentiality will be followed at all times. All researchers will be fully trained in NHS Confidentiality and GCP. Participants' GP practices will be informed that they are taking part in the study.

All paper data will be held in secure locked environments in the office of the Research & Development department in the Carlisle, Whitehaven and Penrith hospital locations. Data released (e.g. by publication) will contain no information that could lead to the identification of an individual participant. Upon completion of the study the site files will be archived for a period of 10 years in line with local archiving policy and procedures. Direct access to data only will be granted to authorised representatives from the sponsor / host institution, grant funder and medical device provider (Milliken Healthcare Inc) and the regulatory authorities to permit trial-related monitoring, audits and inspections.

This investigator-initiated trial will be monitored in terms of conduct of the study by the in-house research team, led by the Chief Investigator, who will convene on a monthly basis in person or via phone/e-mail. A trial steering committee will not be convened for this trial. The study can be audited by the in-house R&D department as part of their rolling audit programme of sponsored and hosted

research studies. As part of the research grant agreement, anonymised study data will be shared with Milliken Healthcare Inc for review and for potential publication purposes. No identifiable data, including on potential exemplar case photos, will be contained in any of this data.

## **10. GOVERANCE OF STUDY**

#### 10.1 Approvals

This study will be conducted in compliance with the protocol approved by the Health Research Authority, National Research Ethics Service, and local Trust R&D Approval, and according to Good Clinical Practice standards including the Declaration of Helsinki (1964, Amended Oct 2013). No deviation from the protocol will be implemented without the prior review and approval of the aforementioned review bodies, except where it may be necessary to eliminate an immediate hazard to a research subject. In such case, the deviation will be reported according to policies and procedures

## 10.2 Sponsor & Indemnity

North Cumbria Integrated Care NHS Foundation Trust is the sponsor of this study and therefore NHS indemnity applies for design, conduct and management of the study. Milliken Healthcare Inc has provided a grant for this study by means of provision of the Andoflex TLC Calamine Lite dressing free of charge and a monetary grant worth £8526.

Patients will not be given financial incentives for taking part in the study. Travel expenses are not offered in this study since patients are seen at their home by community nurses or in clinic as part of their normal care pathway.

## **11. PUBLICATION AND DATA-SHARING POLICY**

The study will be registered on the ISRCTN website, in line with CONSORT guidelines on good practice in clinical research.

The results of this study will potentially be disseminated through:

- Peer-reviewed manuscript in scientific journal
- Conference paper
- Internal report

## APPENDIX 1. OUTCOME MEASURE TOOLS AND ASSESSMENTS

This appendix contains:

- The PUSH tool that will be used to assess ulcer (from Stotts et al, 2001)
- The VEINES Quality of Life survey (from Lamping et al, 2003)
- Visual analogue pain scale and the visual analogue pruritis scale (used in APRICOT study; Jonker et al, 2020)
- Patient feedback and compliance (non-validated)
- EQ-5D-5L quality of life score (from Herdman edt al, 2011)

## Pressure Ulcer Scale for Healing (PUSH) PUSH Tool 3.0

Patient Name	Patient ID#
Ulcer Location	Date

#### **Directions:**

Observe and measure the pressure ulcer. Categorize the ulcer with respect to surface area, exudate, and type of wound tissue. Record a sub-score for each of these ulcer characteristics. Add the sub-scores to obtain the total score. A comparison of total scores measured over time provides an indication of the improvement or deterioration in pressure ulcer healing.

LENGTH	0	1	2	3	4	5	Sub-score
X	0	< 0.3	0.3 – 0.6	0.7 – 1.0	1.1 – 2.0	2.1 – 3.0	
WIDTH		6	7	8	9	10	
(in cm²)		3.1 – 4.0	4.1 - 8.0	8.1 – 12.0	12.1 - 24.0	> 24.0	
EXUDATE	0	1	2	3			Sub-score
AMOUNT	None	Light	Moderate	Heavy			
TISSUE	0	1	2	3	4		Sub-score
TYPE	Closed	Epithelial Tissue	Granulation Tissue	Slough	Necrotic Tissue		
							TOTAL SCORE

#### Veines QoL questionnaire

#### INSTRUCTIONS HOW TO ANSWER:

Answer every question by marking the answer as indicated. If you are unsure about how to answer a question, please give the best answer you can.

## Below are some questions about your views about your legs. This information will help keep track of how you feel and how well you are able to do your usual activities.

	(check one box on each line)	Every day	Several times a week	About once a week	Less than once a week	Never
1.	Heavy legs	1	2	3	4	5
2.	Aching legs	1	2	3	4	5
3.	Swelling	1	2	3	4	5
4.	Night cramps	1	2	3	- 4	5
5.	Heat or burning sensation	1	2	3	4	5
6.	Restless legs	1	2	3	4	5
7.	Throbbing	1	2	3	4	5
8.	Itching	1	2	3	4	5
9.	Tingling sensation (e.g.pins and needles)	1	2	3	4	5

2.	At what time of day is your leg problem most intense	a? (ch	eck one)
	1 On waking	4	During the night
	2 At mid-day	5	At any time of day
	3 At the end of the day	6	Never
			· · · · · · · · · · · · · · · · · · ·

#### 3. Compared to one year ago, how would you rate your leg problem in general now? (check one)

- 1 Much better now than one year ago
- 4 Somewhat worse now than one year ago
- 2 Somewhat better now than one year ago 5 Much worse now than one year ago
- 3 About the same now as one year ago
- 6 I did not have any leg problem last year

## 4. The following items are about activities that you might do in a typical day. Does your leg problem now limit you in these activities? If so, how much ?

	(Check one box on each line)	l do not work	YES, Limited A Lot	YES, Limited A Little	NO, Not Limited At All
a.	Daily activities at work	0	1	2	3
b.	Daily activities at home (e.g. housework, ironing, doing odd jobs/repairs around the house, gardening, etc)		1	2	3
C.	Social or leisure activities in which you are standing for long periods (e.g. parties, weddings, taking public transportation, shopping, etc)		1	2	3
d.	Social or leisure activities in which you are sitting for long periods (e.g. going to the cinema or the theater, travelling, etc)		1	2	3

## 5. During the past 4 weeks, have you had any of the following problems with your work or other regular daily activities as a result of your **leg problem**?

	(check one box on each line)	YES	NO
a.	Cut down the amount of time you spent on work or other activities	1	2
b.	Accomplished less than you would like	1	2
C.	Were limited in the kind of work or other activities	1	2
d.	Had difficulty performing the work or other activities (for example, it took extra effort)	1	2

## 6. During the past 4 weeks, to what extent has your leg problem interfered with your normal social activities with family, friends, neighbors or groups? (check one)

1	Not at all	4	Quite a bit
2	Slightly	5	Extremely
3	Moderately		

7. How much leg pain have you had during the past 4 weeks? (check one)

1 None 2 Very mild

Moderate 4

5

- 3 Mild

Severe Very severe 6

#### 8. These questions are about how you feel and how things have been with you during the past 4 weeks as a result of your leg problem. For each question, please give the one answer that comes closest to the way you have been feeling. How much of the time during the past 4 weeks -

	(check one box on each line)	All of the Time	Most of the Time	A Good Bit of the Time	Some of the Time	A Little of the Time	None of the Time
a.	Have you felt concerned about the appearance of your leg(s) ?	1	2	3	4	5	6
b.	Have you felt irritable ?	1	2	3	4	5	6
C.	Have you felt a burden to your family or friends?	1	2	3	4	5	6
d.	Have you been worried about bumping into things ?	1	2	3	4	5	6
e.	Has the appearance of your leg(s) influenced your choice of clothing ?	1	2	3	4	5	6

